A new closure technique of OCA closure using a self-adhering mesh (Dermabond Prineo®) was developed that further decreased operative times and had similar outcomes. Parvizi et al showed benefits including that patients could shower immediately, could be removed easily with less pain after healing, forms a microbial barrier, provides even tension distribution across the wound, and reduced subcutaneous closure time compared to monocryl with steri strips [13]. Additionally, since the time in the operating room was less, the Prineo was found to be overall less expensive [13]. Richter et al also showed that while Prineo provided equivalent skin approximation compared to intradermal sutures, it was 4.5 times faster to apply and resulted with similar incision healing and cosmetic outcomes [14]. With positive results seen in the literature, Prineo dressings have been increasingly used in total hip and knee replacements. Holte et al evaluated a 2.5 year period with 360 consecutive primary total knees by one surgeon and showed that use of Prineo was successful for high tension total knee wounds, with no cases of wound dehiscence, operative intervention, or prosthetic joint infection [15]. Sutton evaluated the cost-effectiveness of Prineo compared to skin staples and found that Prineo was associated with a shorter length of stay, fewer discharges to rehab, and lower rates of allcause readmission [16].

The goal of this study is to compare conventional methods of wound closure after total shoulder arthroplasty, such as monocryl and dermabond, to a OCA mesh closure technique and evaluate its success.

Objective and Hypothesis:

The objective is to compare two types of wound closure after total shoulder arthroplasty to determine which closure is faster, and subsequently if there are different outcomes between the two types of closures.

The objective of this study is to compare two types of wound closure after total shoulder arthroplasty procedures. A single fellowship trained shoulder surgeon will perform all procedures. We hypothesize that patients who undergo an OCA mesh closure will have a faster closure time, lower cost, non-inferior complication rate, and non-inferior patient satisfaction scores with respect to their postoperative follow up and scar appearance.

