 - Wound cosmesis
 - Patient and Observer Scar Assessment Scale (POSAS)
 - Wound complications (i.e. dehiscence)
 - Wound drainage
 - Infection (superficial vs. deep)
 - Length of stay in hospital
- Endpoints
 - o Primary endpoint is to determine which method of closure is faster
 - Secondary endpoints will include cost of closure, difference in wound complications, aesthetic differences, and difference in patient satisfaction
- Independent Variables
 - o Age
 - o BMI
 - o Race
 - o Gender
 - Length of Incision
 - Depth of Incision
 - o Prealbumin
 - o Albumin
 - o Glucose
- Randomization and blinding
 - A random number generator will be used to assign patients to the study and control groups. Patients will not be notified which group they had been assigned to, though they may be able to determine which group they are in after looking at their wound.

Study Protocol:

20 total shoulder replacement patients presenting to Wakefield Medical Center will be screened for eligibility according to the inclusion and exclusion criteria by study personnel. Medical history and demographic data will be collected and assessed to ensure

that patients meet the inclusion and exclusion criteria. Eligible subjects will be enrolled after informed consent is obtained.

- Prospective Randomized Design
 - After determining a patients' eligibility for inclusion, they will be randomized to the OCA mesh group or monocryl with dermabond group. After surgery, both groups will be seen at their 2 week, 6 week, and 3 month appointment.
- Surveys
 - At the 6 week, and 3 month follow up appointment both groups and the same surgeon will complete a patient observer and scar assessment scale survey
 - The Patient Observer and Scar Assessment Scale validated instrument created to measure patients and physician overall satisfaction with surgical wound appearance / healing [17]
- Data Collection

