 - For each enrolled subject, we will collect data from hospital presentation to discharge on standard demographics, routine laboratory results, clinical information, past medical history and hospital course data (length of stay, mobilization status, associated inpatient procedures and complications). Major complications are defined as: all-cause re-hospitalization, re-hospitalization relating to index surgery, DVT, PE, deep wound infection, dislocation, fracture, death. Minor complications include: UTI, delayed wound healing, superficial wound infection. Complications resulting from the surgery will be distinguished from those resulting from pre-existing conditions and comorbid states.
 - All the data will be recorded and stored in a password-protected Excel spreadsheet on study personnel password-protected work computers.
- Statistical Considerations
 - o Power Analysis
 - Power Power analysis (IBM SPSS 21) was performed before the study at a level of 0.05 alpha error and 0.8 beta error. Looking at closure time of total shoulder arthroplasty wounds, looking for an effect size of 13 minutes between closure groups determined that a sample size of 2 patients in each group was adequate to detect significant differences in closure times between groups. Increasing group size to 5 patients in each group resulted in a power of 88% at an alpha of 0.05 and using 10 patients in each group resulted in 100% power at an alpha of 0.05.

Measures to address study aims:

To address specific aim 1: We will first measure the length of the incision and depth of the wound with a intraoperative flexible ruler prior to closure. We will assess the timing of closure in the operating room by the surgeon announcing the start of closure. At this time, the circulating nurse will start monitoring time with a stopwatch. Once the dressings are completely on, the surgeon will announce to end time and the circulating nurse will stop the stopwatch. The timing of closure will be recorded.

To address specific aim 2: We will compare the costs of the two closure methods by determining the cost of the medical supplies used for closure, as well as calculating the cost of the operating room time that was required for each closure. The sum of these costs will be the total cost of closure.

To address specific aim 3: We will compare complications, including drainage and infection, between the groups over a 3 month period.

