To address specific aim 4: We will compare POSAS scores between the study group and control group at the 6-week postoperative follow up visit and 3 month postoperative follow-up visit.

Informed Consent

Informed consent procedure will take place during the preoperative consultation in the clinic setting or at any point during the hospital admission where the procedure is to be performed. This consent process will occur prior to the day of surgery. Study personnel including [name], [name], or [name] will approach patients in a manner, time, and location that insure participant privacy. Information about the study will be conveyed to the participant in simple understandable English. The information that will be provided to prospective subjects will include the studies purpose, the risks associated with the study, the potential benefits of the study, study requirements, and a request for compliance with study procedures.

Ample time and opportunity for patients to consider all options and ask questions will be given before signing the informed consent form. All participants' questions will be answered. Verbal confirmation that the participant has comprehended the information and options provided will be obtained through Talk Back technique.

Upon agreeing to participate in the study, patients will provide written consent using an IRB-approved informed consent document. Enrolled subjects will be provided with copies of signed consent documents. Efforts will be made to continue to provide information and options as the participant or research requires.

Safety Considerations

Total joint arthroplasty closure techniques vary widely based on surgeon preference and practices. In shoulder arthroplasty, closure with monocryl suture, dermabond, nylon suture, and staples have all been used. In total joint arthroplasty, OCA mesh closure is also used. Safety risks of the OCA mesh may include wound dehiscence, drainage, infection and need for re-operation. However, these risks are minimal and should not be significantly different in the control and study groups. If there is any concern that the OCA mesh is leading to increased complications, the study will be abandoned. Additionally, if there are indications of wound complications that need alternative treatment, including revision closure, the study will be abandoned. Pregnancy testing will be done as part of the normal preoperative labs in women of child-bearing age.

Confidentiality of Research Records

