The signed assurances of the PI ([name]) included in the CCI/IRB Research Application form, including the policy for reporting internal and external adverse events should constitute a sufficient plan. Additionally, as a single site and small numbers of study subjects, close monitoring every 3 months by the study investigators ([name] and [name]) should be adequate as well. An independent data safety monitor will be appointed..

Project Management

[name] – Primary Investigator – will be responsible for the research protocol, study implementation plan, obtaining consent from eligible patients, and data analysis and interpretation

[name] – Primary Resident Investigator – will be responsible for the research protocol, study implementation plan, subject screening, obtaining consent from eligible patients, data collection and analysis, and coordination between different departments and ancillary services.

[name] – Secondary Resident Investigator - will be responsible for the research protocol, study implementation plan, subject screening, obtaining consent from eligible patients, data collection and analysis, and coordination between different departments and ancillary services.

Expected Outcomes

The expected Outcomes of this randomized prospective study is faster closure times and non-inferior complication rates with equivalent patient satisfaction for the OCA mesh group compared to the conventional closure group. There is no expected increase in adverse outcomes for the OSA mesh group.

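### The observer scar score is given by the operating surgeon, who knows the arm, and the plan does not separate it from the patients' own score

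*Combined protocol and SAP*

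**What the plan says.** The Objective and Hypothesis section states: "A single fellowship trained shoulder surgeon will perform all procedures". Under Measures to address study aims, aim 1, timing begins with the "surgeon announcing the start of closure", and the surgeon also calls the end. In the Study Protocol section, under Surveys, at 6 weeks and 3 months "both groups and the same surgeon will complete a patient observer and scar assessment scale survey". The same place describes POSAS as a "validated instrument created to measure patients and physician overall satisfaction with surgical wound appearance / healing", so it has a patient part and a physician part.

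The only blinding text, under Randomization and blinding, is about patients: "Patients will not be notified which group they had been assigned to, though they may be able to determine which group they are in". Under Endpoints, cosmesis is secondary: "Secondary endpoints will include cost of closure, difference in wound complications, aesthetic differences, and difference in patient satisfaction". For aim 4 the analysis is stated as "We will compare POSAS scores between the study group and control group at the 6-week postoperative follow up visit", and again at 3 months. No test is named, and nothing says whether the two parts are kept apart or combined. Project Management lists two resident investigators whose duties include "subject screening, obtaining consent from eligible patients, data collection and analysis".

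**The concern.** The observer part of POSAS is a judgement, not a measurement, and it is made by a person who knows which closure each patient received. The plan also declares the answer it expects: its hypothesis is that the mesh scar will be no worse. A rater in that position can shift scores without intending to.

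POSAS is the only cosmesis instrument named, and the Specific Goal makes the aesthetic result one of the four grounds for a closure recommendation. If the two parts are reported as one result, a reader cannot tell whether it came from the patients or from the surgeon. At stake is the credibility of the scar conclusion, not that of the closure-time comparison.

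**Working it through.** **Does the rater know the arm?** Three statements settle this.

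1. One surgeon does all procedures (Objective and Hypothesis).
2. That surgeon announces the start and end of closure (aim 1), and so sees the closure used.
3. The same surgeon completes the scar survey at both visits (Surveys).

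That the surgeon personally places the closure is a natural inference, though the plan does not say so outright. Knowledge of the arm does not depend on it. The documents mention no masked assessor, second rater or rating from photographs.

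**Could someone else rate?** Both visits already take place, and two residents already have data-collection duties. With 20 to 22 patients and two visits, the task is 20 × 2 = 40 to 22 × 2 = 44 ratings. The documents do not say whether either resident attends the operations. They place the allocation file on the computer of a person whose name is removed, so it is not known whether a resident holds it.

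**How large could the effect be?** The plan gives no figure to reproduce, so this is an illustration under assumptions.

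- Arm size n: 10 or 11, because the plan gives both 20 and 22 as the total. Equal arms are assumed.
- Test: two-sided 5% two-sample t-test of superiority, assumed because none is named.
- Truth: no difference between arms.
- Shift b: the rater moves observer scores toward one arm by b SD. The values 0.25 and 0.5 are assumptions.

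The test statistic then follows a noncentral t distribution with 2n − 2 degrees of freedom and noncentrality b × √(n/2). The false-positive rate is the probability that it falls beyond either critical value.

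| n per arm | b | Noncentrality | False-positive rate |
|---|---|---|---|
| 10 | 0.25 | 0.25 × √5 = 0.56 | 8.3% |
| 11 | 0.25 | 0.25 × √5.5 = 0.59 | 8.6% |
| 10 | 0.5 | 0.5 × √5 = 1.12 | 18.5% |
| 11 | 0.5 | 0.5 × √5.5 = 1.17 | 20.1% |

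**If the two scales were averaged with equal weight** (also an assumption), only half of the score carries the shift. With correlation r between the scales, the standardised shift is (b/2) / √((1 + r)/2). At 11 per arm:

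- b = 0.25: shift 0.155 (r = 0.3) to 0.136 (r = 0.7); false-positive rate 6.4% to 6.1%.
- b = 0.5: shift 0.310 (r = 0.3) to 0.271 (r = 0.7); false-positive rate 10.7% to 9.3%.

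Averaging dilutes the shift but also conceals where it came from.

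**The case against.** The strongest reply is that these percentages do not measure the plan's own claim. The scar claim is non-inferiority, with no margin and no named test, so its error rate cannot be computed. A rater who pulled the arms toward equality would make a false difference less likely, not more. This stands: the figures show only how sensitive a small comparison is to a one-sided shift.

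A second reply is that sample size matters more. By the same calculation, with 11 per arm the power to detect a true 0.5 SD difference is about 20%, so even a masked rater would miss it about 80% of the time. That is correct, but low precision does not excuse a bias that can be reduced.

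Third, a single constant rater avoids between-rater variation. That is a real advantage, and it is kept if the masked rater is also the same person throughout.

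Fourth, a reader might infer that half of the cosmesis outcome is compromised, or that the plan merges the two scores. The documents support neither. They give no weighting and no total, and they list aesthetic differences and patient satisfaction as separate endpoints. The plan is silent on combination.

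Fifth, a reader might infer that the existing team could remove the bias. That is too strong. Both residents have wide duties and neither is described as masked. The scar itself may reveal the closure. Nor is the patient scale a clean refuge, since the plan concedes that patients may work out their group.

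**Conclusion.** The point holds as a limited one. As written, the plan gives an unmasked observer score on a subjective secondary outcome, and an aim 4 analysis that does not keep that score apart from the patients' own. The aesthetic part of the recommendation is exposed to assessor bias that could be reduced with staff already on the study. The primary endpoint is unaffected by this point.

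The size of the bias cannot be derived from the documents. The illustrative range, about 8% to 20% for the observer scale alone and about 6% to 11% for an average, rests on the assumed shifts, equal arms, a superiority t-test and, for the average, a correlation of 0.3 to 0.7. It should not be read as the error rate of the trial's non-inferiority conclusion. The change is worth making before scores are seen, but the trial does not stand or fall on it.

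**What to change.** In the Study Protocol section, under Surveys, have the observer scale completed at both visits by one of the resident investigators, the same one for all patients. That resident should stay out of the operating room for enrolled cases, should not collect closure-time, supply-cost or 2-week wound data, and should have no access to the allocation file. State that this reduces the bias and may not remove it, because the scar may show which closure was used.

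Under aim 4, whether or not a masked rater proves feasible:

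- analyse and report the patient and observer scales separately;
- label any surgeon-scored observer data as unblinded and supportive;
- do not rest the aesthetic conclusion on surgeon-scored data alone;
- state that patients may also have identified their group.

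The aim 4 changes cost only wording. The masked rater needs no new staff or visits, but it restricts that resident's other study duties and operating-room attendance, so some of that work would pass to other team members.

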Patients in the OCA mesh cohort will be compared to patients who have a closure with a running monocryl suture and dermabond. This investigation seeks to determine if OCA closure mesh closure is non-inferior to monocryl suture and dermabond in terms of operative time, cost, complications, and aesthetic appearance.

If the hypothesis is confirmed, this study will suggest that a OCA mesh closure may be used for total shoulder arthroplasty surgeries as an alternative to current conventional closures and may provide a cost benefit.

Specific Goal:

1) To specifically be able to make a recommendation of total shoulder wound closure based on complications, aesthetic result, time to closure, and cost

Specific Aims:

- 1) To compare the timing of total shoulder closure between OCA mesh and monocryl/dermabond closure
- 2) To compare the costs of the OCA mesh closure versus monocryl/dermabond
- 3) To compare the complications the OCA mesh closure versus monocryl/dermabond closure
- 4) To compare the healing and patient satisfaction of wounds between the OCA mesh closure versus monocryl/dermabond closure

Study Plan:

The study will be implemented at the Wakefield Campus of Montefiore medical center by randomizing patients undergoing total shoulder arthroplasty to receiving closure with monocryl and dermabond versus dermabond with self-adhering mesh. Participants will be subsequently followed for 3 months to evaluate wound healing and monitor for complications.

Methods:

- Design Prospective randomized intervention
- Setting Wakefield Hospital of Montefiore Medical Center
- Participants Patients who agree to participate in the study undergoing total shoulder arthroplasty
- Study Period
 - \circ Sample size 22 patients
 - Determine using a standard between-groups sample size calculation with a type 1 error rate of 5% and 80% power to detect a moderate effect size (0.5 standard deviation)
 - o Inclusion
 - Total shoulder arthroplasty
 - Reverse total shoulder arthroplasty

- Age 18-100
- Single Surgeon
- o Exclusion
 - Previous shoulder surgery
 - Known wound healing complications
 - DM, chronic steroid use, vascular insufficiency, morbid obesity (BMI>40), ESRD, family hx of pathologic scars
 - Patients on blood thinners (ASA 81mg ok)
 - Connective tissue disease
 - Allergy to skin adhesive
 - Mentally unable to complete questionnaires
 - Previous wound over planned incision
- Measures
 - o Time for closure
 - Cost of closure (time in OR, materials)

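### The Power Analysis inverts the type 2 error and calls 2 patients per group adequate, although its own 88% at 5 per group implies 26% (at most 56%) power at 2 per group

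*Combined protocol and SAP*

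**What the plan says.** The protocol justifies its size in two places.

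- **Statistical Considerations, Power Analysis.** The calculation "was performed before the study at a level of 0.05 alpha error and 0.8 beta error". For a 13-minute difference in closure time it finds that "a sample size of 2 patients in each group was adequate to detect significant differences in closure times between groups". It then reports 88% power for groups of 5 and, for groups twice that size, says that "using 10 patients in each group resulted in 100% power at an alpha of 0.05". It names the software but gives no SD, test or sidedness.
- **Methods, Sample size.** The entry reads "Sample size 22 patients" and attributes this to a between-groups calculation with a 5% type 1 error and "80% power to detect a moderate effect size (0.5 standard deviation". It does not name the endpoint to which the half-SD effect applies.

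The Study Protocol section gives a slightly different number: "20 total shoulder replacement patients presenting to Wakefield Medical Center will be screened for eligibility". The plan is therefore for about 10 or 11 per group. Endpoints makes speed of closure the primary endpoint.

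**The concern.** Beta is the probability of missing a true effect, so a beta of 0.8 is 20% power. That contradicts the 80% under Methods. If it is a slip for 80% power, the 2-per-group statement has to be judged against 80%, and it sits badly beside 88% at 5 per group: power climbs steeply at these sizes, and a design with 80% at 2 per group should be close to certain at 5.

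This is the only power statement tied to the primary endpoint. As it stands, a reader cannot tell which error rate, effect, SD or test supports the sample size, and the two sections appear to support it with different effects.

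**Working it through.** **Inputs.** From the Power Analysis: alpha 0.05, difference 13 minutes, 88% power at n = 5 per group, 100% at n = 10, and 2 per group called adequate. From Methods: 80% power, 0.5 SD, 22 patients. Equal groups are implied. SD, test and sidedness are not stated, so four standard variants were tried.

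**Formulas**, with d = 13/SD and n per group:

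- t-test: power is the probability that a noncentral t with 2n − 2 degrees of freedom and noncentrality d√(n/2) passes the critical value.
- Normal approximation: power = Φ(d√(n/2) − z), with z = 1.960 (two-sided) or 1.645 (one-sided).

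**Step 1: fit the plan's own 88% at 5 per group, then check its 100% at 10.** For the two-sided t-test, d = 2.269 (SD 13/2.269 = 5.73 min) gives 88%: df = 8, noncentrality 2.269 × √2.5 = 3.588. The same d gives 99.8% at 10 per group, which rounds to the stated 100%. The 88% and the 100% therefore agree with each other.

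**Step 2: same d, n = 2.** Here √(n/2) = 1, so the noncentrality is d itself. For the two-sided t-test it is 2.269 against a critical value of 4.303 on 2 df, and power is 26.1%. For the two-sided normal, Φ(1.983 − 1.960) = Φ(0.023) = 50.9%. For the one-sided normal, Φ(1.783 − 1.645) = Φ(0.138) = 55.5%.

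| Variant, fitted to 88% at n = 5 | d | SD (min) | n = 2 | n = 4 | n = 10 |
|---|---|---|---|---|---|
| Two-sided t | 2.269 | 5.73 | 26.1% | 76.2% | 99.8% |
| One-sided t | 1.958 | 6.64 | 37.4% | 78.7% | 99.5% |
| Two-sided normal | 1.983 | 6.56 | 50.9% | 80.1% | 99.3% |
| One-sided normal | 1.783 | 7.29 | 55.5% | 81.0% | 99.0% |

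The smallest size reaching 80% is 5 per group by t-test and 4 by normal approximation. If the 88% was rounded from anywhere between 87.5% and 88.5%, the two-sided t figure at n = 2 moves only between 25.8% and 26.4%, and the one-sided normal figure reaches at most 56.1%. A simulation of 400,000 trials gives 26.2% for the pooled two-sided t-test.

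**Step 3: reverse check.** Suppose 2 per group really had 80% power. The SD would be 2.30, 3.27, 4.64 or 5.23 min (variants in the table's order), and power at 5 per group would be above 99.9%, above 99.9%, 99.3% or 98.9%. None is 88%.

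**Step 4: the half-SD effect under Methods (two-sided t).** At 11 per group the noncentrality is 0.5 × √5.5 = 1.173 and power is 20.1%; at 10 per group it is 18.5%. Power of 80% needs 64 per group, 128 in total (63 gives 79.5%). One-sided, 11 per group gives 30.4%.

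**Step 5: what the planned size can detect.** With 80% power (two-sided t), 11 per group detects 1.256 SD and 10 per group detects 1.325 SD. For 13 minutes that holds for any SD up to 13/1.256 = 10.4 min, or 13/1.325 = 9.8 min.

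**The case against.** The strongest reply is that the two charges in the Power Analysis belong to different readings. If beta really was set at 0.8, the target was 20% power; 2 per group passes it (26.1%), and the sequence of 2, 88% at 5 and 100% at 10 is coherent under a two-sided t-test. The half-SD figure points the same way, since 11 per group is the smallest size that reaches 20% power at 0.5 SD, and 11 per group is 22 patients. One inverted input could explain both sections. If instead 0.8 is a slip for power, only the 2-per-group sentence is wrong.

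This is a fair account of how the error may have arisen, and a good reason to look at the original input before editing. It does not rescue the text. On the literal reading the target contradicts the 80% under Methods; on the slip reading 2 per group is not adequate.

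Four further points carry some weight.

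- The check assumes that the same inputs lie behind successive sentences. That is reasonable but unstated.
- The upper bound of 56% comes from a variant that fits the stated 100% at 10 per group less well (99.0%). The best-fitting variant, the two-sided t, gives the lowest of the four figures.
- Methods does not tie the half-SD effect to closure time, so the mismatch of effects is a related but separate fault.
- Nobody proposes to enrol 2 per group. This limits the consequence but does not correct the statement.

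**Conclusion.** The concern holds. A beta of 0.8 conflicts with the stated 80% power, and calling 2 per group adequate conflicts with the 88% given for 5 per group: power at 2 per group is 26% to 56% depending on test and sidedness, a shortfall of 24 to 54 points against 80%. Separately, 22 patients give about 20% power at 0.5 SD (two-sided t), not 80%.

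The 2-per-group result rests on the plan's own 88%, equal groups and a common set of inputs; no SD was assumed. The half-SD result needs only the test and equal groups.

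The impact is limited. At the effect implied by the 88%, 10 or 11 per group has about 99% power or more, so the primary comparison is not shown to be underpowered for 13 minutes. That reassurance is itself back-solved, and the documents contain no SD to confirm it. This should be fixed, but it does not threaten the design.

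**What to change.** 1. Retrieve the original calculation and establish which SD, test, sidedness and beta were entered.
2. In the Power Analysis, replace the 0.8 type 2 error with power 0.80 (beta 0.20). State the test, the sidedness, the SD and its source. Rerun from those inputs and report power at the planned group size. Do not adopt an SD back-solved from the 88%.
3. Delete the sentence that calls 2 per group adequate.
4. Reconcile the Power Analysis and the Sample size item to one target effect for closure time. The better course is to base the size on a supported 13-minute calculation and cite it under Methods. If 0.5 SD stays there, the stated 80% must become about 20% for 22 patients (two-sided t), which would openly declare weak power for that effect.
5. Use one planned total; the text now gives both 22 and 20.

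The cost is protocol wording and one rerun. Enrolment need not change for the 13-minute target, provided the sourced SD is no more than about 10.4 min with 11 per group, or 9.8 min with 10 per group.

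### Does closure time need a prespecified analysis adjusted for incision length?

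*Combined protocol and SAP*

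**What the plan says.** Under Methods, Endpoints: "Primary endpoint is to determine which method of closure is faster". Specific aim 1 describes how the data are obtained: "We will first measure the length of the incision and depth of the wound with a intraoperative flexible ruler prior to closure", followed by stopwatch timing from the announced start of closure until the dressings are on. "Length of Incision" is one of nine items under Independent Variables; nothing says how any of them enters an analysis.

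Statistical Considerations contains only a power analysis, "looking for an effect size of 13 minutes between closure groups". It states that "a sample size of 2 patients in each group was adequate", that "Increasing group size to 5 patients in each group resulted in a power of 88% at an alpha of 0.05", and that 10 per group gives 100%. No SD for closure time and no correlation between length and time is given.

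On timing and masking: "After determining a patients' eligibility for inclusion, they will be randomized to the OCA mesh group or monocryl with dermabond group", so allocation precedes the ruler measurement. "Patients will not be notified which group they had been assigned to" concerns patients only; the plan does not say when the surgeon learns the arm.

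**The concern.** A primary endpoint with no named analysis leaves a choice open. Incision length is recorded for every patient just before the clock starts, a running suture is laid along the incision, and a longer wound should plausibly take longer to close. With 10 or 11 patients per arm, chance alone produces a length difference above 0.5 SD in about 24-26% of trials. An analyst could thus fit the model with and without length and report the more favourable result. Naming length as the single covariate in advance would remove that freedom and might narrow the interval for the minutes saved, which also feeds the cost comparison under aim 2.

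**Working it through.** **Inputs.** From the documents: a 13-minute difference, alpha 0.05, the stated powers at 2, 5 and 10 per group, and a total of 22 (Methods) or 20 (Study Protocol). Assumed: two-sided tests, equal arms, normal data, and a within-arm length-time correlation r between 0 and 0.7.

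**1. The plan's own figures.** For a two-sided t test, 88% power at 5 per group requires d = 2.269, so SD = 13/2.269 = 5.73 minutes. That SD gives 99.8% at 10 per group, in line with the stated 100%, and 99.9% at 11. It gives only 26% at 2 per group; 80% there would need SD = 13/5.653 = 2.3 minutes. These statements disagree with each other, but that is a sample-size matter and adjustment does not resolve it.

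**2. What adjustment does to the CI, common slope.** The ratio of adjusted to unadjusted average width is approximately

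[t(N-3)/t(N-2)] x sqrt(1 + 1/(N-4)) x sqrt(1 - r²).

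For N = 22: (2.093/2.086) x sqrt(1 + 1/18) = 1.003 x 1.027 = 1.031 before the last factor.

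| r | sqrt(1 - r²) | formula | simulation |
|---|---|---|---|
| 0 | 1.000 | 1.031 | 1.029 |
| 0.3 | 0.954 | 0.983 | 0.982 |
| 0.5 | 0.866 | 0.893 | 0.892 |
| 0.7 | 0.714 | 0.736 | 0.734 |

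Break-even is r of about 0.24 (N = 22) or 0.25 (N = 20). These are averages: at r = 0.25 a single trial of 22 gets a narrower interval only 42% of the time.

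**3. If minutes per cm differ by arm.** The Background cites a study in which mesh was 4.5 times faster to apply. Treating that as a slope ratio is an assumption, since it is a speed and not minutes per cm. Let r be the suture-arm correlation, with equal residual SDs and unit total variance in the suture arm. The slopes are r and r/4.5, with mean 0.611r and half-difference 0.389r. The variance about the fitted common line is 1 - r² + (0.389r)² = 1 - 0.849r². The pooled unadjusted variance is 1 - r² + (r² + r²/20.25)/2 = 1 - 0.475r². At r = 0.5 the ratio is 1.031 x sqrt(0.788/0.881) = 0.975 (simulation 0.973). At r = 0.3 it is 1.013 (simulation 1.011), and at r = 0.7 it is 0.900 (simulation 0.896). Break-even in the suture arm is 0.37-0.39. Other variance assumptions with the same slope ratio give 0.28-0.41.

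**4. In minutes, N = 22.** The average unadjusted half-width is 0.878 SD; adjusted at r = 0.5 with a common slope it is 0.784 SD.

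- SD 5.73: 5.03 to 4.49 minutes. Around an estimate of 13, the interval is about 8.0 to 18.0 unadjusted and 8.5 to 17.5 adjusted.
- SD 2.3: 2.02 to 1.80 minutes.
- SD 26 (if 13 minutes were the 0.5 SD of the Methods calculation, a link the plan never makes): 22.8 to 20.4 minutes. Power goes from 20% to 24%.

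Under none of these readings does the covariate change whether 13 minutes would be detected with reasonable certainty.

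**5. The cost of leaving the choice open.** With no true difference and N = 22, taking the smaller of the two p-values rejects in 5.9%, 7.3% and 8.3% of trials for r = 0, 0.5 and 0.7 (common slope). Either analysis used alone holds 5%.

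**6. What adjustment would risk.** If knowledge of the arm shifted recorded length by 0.25 SD, the adjusted difference would move by 0.25r SD of closure time. At r = 0.5 and SD 5.73 that is 0.125 x 5.73 = 0.7 minutes, more than the 5.03 - 4.49 = 0.5 minutes gained in half-width.

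**The case for a change.** The strongest case for a change is that the omission is real, the inflation to 6-8% is reproducible, the covariate is already collected, and one sentence would settle the matter. A nine-item list with no stated role also invites an overloaded model: entering all nine would leave 22 - 2 - 9 = 11 residual degrees of freedom, or 9 with 20 patients.

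It stands that no test is named. It also stands that the Objective and Hypothesis section speaks both of a faster closure and of non-inferiority in operative time. A confidence interval for the difference in minutes serves both readings: if it lies wholly on the side of faster closure with mesh, non-inferiority follows for any margin.

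The case for length in particular does not stand. Naming either analysis would remove the inflation, so it gives no reason to prefer the adjusted one. Precision is the only such reason, and it rests on a correlation the documents do not supply. The timed interval runs through application of the dressings, part of which need not scale with length. Nor would a length covariate cure other weaknesses. In a simulation with simple randomisation and a mesh residual SD also 4.5 times smaller, type I error was 7.2-7.3% for the adjusted linear model and 7.4-7.5% for the pooled t test, so the two are about equally exposed.

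**Conclusion.** No change follows. The missing sentence is a gap that an analyst fills sensibly: the power analysis describes two groups compared on minutes of closure time at 5%, and the unadjusted difference with its 95% CI is unbiased under randomisation. At the plan's 13 minutes and the SD of 5.73 implied by its 88% figure, power is about 99.9% with 11 per arm, so the conclusion would not hang on the covariate.

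Adjustment for length is a fair trade-off, not a correction. It costs about 3% in average CI width if length is irrelevant and gains 11% at r = 0.5 with a common slope. With a mesh slope 4.5 times flatter and equal residual SDs, the change is +1% at r = 0.3 and -3% at r = 0.5. Against that, it relies on a measurement taken after allocation by a team not described as blinded.

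These figures assume equal arms, normal data and two-sided tests. A much stronger correlation (r = 0.7, common slope) would give a 27% narrower interval, but nothing in the documents supports that value. The conflicts between the stated sample sizes and powers are a separate question.
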